- The **primary outcome** of this study is the proportional change from baseline in VO₂ max from Monday to Friday of week 6, after receiving 7-day or 42-day old blood on the Wednesday of Week 6. We hypothesize that transfusion of RBCs stored for 42 days are less effective at increasing oxygen delivery than RBCs stored for 7 days, which would confirm results from our pilot study where we observed an 82% difference in proportional change between 7- and 42-day VO₂ max study arms. We will test the change scores for normal distribution, and will compare the 42- to 7-day groups using either a student's t-test or Wilcoxon rank sum test in a one sided superiority hypothesis test at the 0.05 significance level. Subjects who withdraw or are excluded before randomization will simply be dropped from analysis. We will further examine the treatment effect by adjusting for potential effects of hemoglobin, and BMI in a linear regression model.
- **Secondary outcomes:** Our secondary outcomes include mean proportional change between 7- and 28-day VO₂ max study arms, and change in duration of exercise between all three groups. Of note, in contrast to the primary endpoint, this secondary analysis is expected to show increases in VO₂ max attributable to intravascular volume expansion and increased hemoglobin mass. Nevertheless, these changes are of interest and it is possible that storage duration may affect VO₂ max acutely after transfusion.

Sample Size: Sample size and power are estimated for a superiority study design using a t-test with a power of 80%, and a one-sided significance level of 0.05. Based on the collected pilot data, we expect the mean percent change VO₂ max for subjects who receive 7-day blood to be 8.7% (SD = 6%), and the mean percent change VO₂ max for subjects who receive 42-day blood to be 1.6% (SD = 6%), providing an effect size of 1.183. Thus, the sample size needed for each group is 10 participants, for a study total of 30. While this calculated sample size may not allow us enough power to test a non-inferiority margin of 20% between the 7 day and 28 day groups, it will provide exploratory evidence for a future trial by providing a more accurate assessment in the variation of the data.

F. FUNDING STATUS, DETAILS

This study is funded by a grant from the National Institutes of Health/NHLBI.

G. HUMAN SUBJECTS RESEARCH PROTECTION FROM RISK

Risks to Subjects

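### Does the primary test lose precision or power by leaving out Monday VO₂ max as a covariate and choosing between t-test and Wilcoxon after a normality check?

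*Combined protocol and SAP*

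**What the plan says.** Everything relevant is in section E (Statistics).

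- **Endpoint.** The primary outcome is the "proportional change from baseline in VO₂ max from Monday to Friday of week 6", compared between the 7-day and 42-day arms. Monday VO₂ max enters as the denominator of that change.
- **Test.** "We will test the change scores for normal distribution" comes first. The comparison is then a Student's "t-test or Wilcoxon rank sum test in a one sided superiority hypothesis test at the 0.05 significance level". The normality test, its cut-off and the data it is applied to (each arm, pooled, or residuals) are not stated.
- **Adjusted analysis.** The treatment effect is examined further by "adjusting for potential effects of hemoglobin, and BMI in a linear regression model". Monday VO₂ max is not listed there.
- **Sample size.** It is computed "using a t-test with a power of 80%, and a one-sided significance level of 0.05", with mean changes of 8.7% and 1.6%, an SD of 6% in each arm, an effect size of 1.183 and 10 subjects per group.

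**The concern.** Two features invite criticism.

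First, baseline adjustment is usually at least as efficient as a change score in large samples. Error in the Monday test stays in the percent change. A chance difference in Monday VO₂ max between two groups of 10 also carries through as regression to the mean. Leaving out a covariate that has already been measured therefore looks like wasted precision in a comparison of only 20 subjects.

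Second, choosing the test after looking at the outcome data can distort the type I error, and the power calculation covers only the t-test. Applied to normal data, the exact Wilcoxon test has about 78% power at the planned effect, below the stated 80%.

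If both points held, the trial would be giving up power and leaving its primary p-value open to choice, when a change of wording would cure both.

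**Working it through.** **Inputs from section E:** mean changes 8.7% and 1.6%, SD 6%, one-sided α = 0.05, 10 per arm.

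**Assumed:** the between-subject SD of VO₂ max, B, taken as 8 to 20%. The documents give neither B nor a Monday-Friday correlation. Section C says only that intra-subject variability over several days is very small.

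**1. The plan's own figure.** Effect size = (8.7 − 1.6)/6 = 1.183. The noncentral t distribution gives n = 9.59 per group, rounded up to 10. Power at 10 per group is 81.6%. The stated sample size reproduces.

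**2. What adjustment saves in large samples.** Treat the whole 6% SD of change as test error. The error variance per test is then 36/2 = 18, and the Monday-Friday correlation is ρ = B²/(B² + 18). The large-sample ratio of adjusted to change-score variance is (1 + ρ)/2.

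**3. What adjustment costs with 20 subjects.** The slope on Monday VO₂ max is estimated from 18 within-arm degrees of freedom. Averaged over chance imbalance, this multiplies the variance by 1 + 1/(18 − 2) = 17/16. The residual degrees of freedom also fall from 18 to 17 (critical t 1.740 instead of 1.734). Counting the lost degree of freedom but not the 17/16 factor gives powers of 82-85%, which are too high.

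| B (assumed) | ρ | (1 + ρ)/2 | × 17/16 | Simulated power, adjusted |
|---|---|---|---|---|
| 8% | 0.78 | 0.89 | 0.95 | 83.5% |
| 12% | 0.89 | 0.94 | 1.00 | 81.4% |
| 16% | 0.93 | 0.97 | 1.03 | 80.4% |
| 20% | 0.96 | 0.98 | 1.04 | 80.1% |

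The unadjusted t-test has about 81.6% throughout.

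**4. Break-even.** Adjustment helps only if (1 + ρ)/2 < 16/17, that is ρ < 15/17 = 0.88. Solving B² = 18 × (15/17)/(2/17) = 135 gives B = 11.6%. Equivalently, Monday VO₂ max must correlate with percent change at |r| above √(1/17) = 0.24. If r = 0, adjusted power is 79.5%.

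**5. The pure-error assumption favours adjustment.** Suppose half of the 36 is true variation in response to transfusion. Error variance per test is then 9, and r² = 9²/[36 × (B² + 9)].

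- B = 8: r² = 81/(36 × 73) = 0.031; net ratio (1 − 0.031) × 17/16 = 1.03.
- B = 20: r² = 81/(36 × 409) = 0.0055; net ratio 1.06.

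Adjustment then loses over the whole assumed range.

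**6. The normality step.** This was simulated with 8,000 trials per setting and 10 per arm, using Shapiro-Wilk at 0.05 as an assumed rule applied to each arm, to residuals, or to pooled data. The Monte Carlo SE of the type I error is about 0.25 points.

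| Data | Type I error: two-stage / t-test | Power at 7.1 points: two-stage / t-test |
|---|---|---|
| Normal | 5.3-5.4% / 5.3% | about 82% / 82% |
| t, 3 df | 4.7-5.2% / 4.4% | 89-91% / 86% |
| Lognormal | 4.8-5.7% / 4.9% | 92-94% / 84% |

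The 78% figure would apply only if Wilcoxon were always used on normal data. The per-arm check sends about 10% of normal data sets there, and the two tests disagree in about 6% of trials. If those two events were unrelated, the conclusion would change in about 0.10 × 0.06 = 0.6% of trials.

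**The case for a change.** The best case for the concern is about a fixed analysis, not average power.

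The rule is incomplete. In simulated normal data at the planned effect, the three readings of the normality check (per arm, pooled, residuals) disagree on which test is primary in 14% of trials. The t-test addresses means and the Wilcoxon test addresses ranks, so the estimand moves with the choice. This stands as a gap in detail. Its effect is bounded: even taking the smaller of the two p-values every time, which the plan does not propose, gives a type I error of about 5.7-6.4%.

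Chance imbalance also matters conditionally. Under the pure-error assumption, a one-standard-error imbalance in Monday VO₂ max shifts the unadjusted difference by 0.4-0.9 points, and a two-standard-error imbalance by 0.8-1.8 points, against a planned 7.1. That is correct given the imbalance. Over randomizations, however, the shift averages to zero, and its spread is already inside the unadjusted standard error of 6 × √(2/10) = 2.7 points. It is not a bias in the planned test.

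Monday VO₂ max would be a legitimate covariate for this comparison. It is measured after randomization but before transfusion, and section D gives cycles A and C the same blood removals. That makes adjustment permissible, not advantageous.

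The alternative has costs of its own. A log-scale model replaces a difference in mean percent change with a ratio of geometric means, which is not the scale of the pilot-based sample size. Making a linear model the only primary test also gives up the protection that the Wilcoxon option offers when the data are skewed or heavy-tailed.

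**Conclusion.** The concern does not hold. The planned comparison is valid and its sample size reproduces (10 per group, 81.6% power). Adjusting for Monday VO₂ max has no demonstrated gain: over an assumed between-subject SD of 8-20%, the effect runs from a 5% reduction in variance to a 4% increase, or about 2 points of power gained to 1.5 points lost. It is less favourable if part of the 6% SD is real variation in response. Which side of break-even the trial falls on depends on a figure the documents do not give. The high repeatability described in section C, if it means a Monday-Friday correlation above 0.88, puts it on the losing side.

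The choice between t-test and Wilcoxon does not materially raise the type I error, matches the t-test's power on normal data and exceeds it on the non-normal data examined. These results assume Shapiro-Wilk at 0.05. What remains is an unnamed normality test and a preference between two defensible analyses.

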Nine subjects were consented but 1 failed screening tests (abnormal pulmonary function testing) and 8 completed the study. There was strong interest from fit habitual exercise enthusiasts to participate in this type of study and enrollment was completed quickly. Subjects in both study arms, encouraged by the same individual ([name]), exercised to exhaustion with high peak heart rates, e.g. mean of 184 ± 5 vs 184 ± 11 . Despite the small sample size (4 per study arm) we observed intriguing differences in VO_2 max ($p=0.2$) and exercise duration ($p=0.02$) between study arms (figures below). Indeed in the 42-day arm, in half of the subjects, VO_2 max and exercise duration actually decreased (was worse) after transfusion with 2 units of 42 day RBCs, whereas all 4 subjects who received 7 day RBCs exhibited increases in these endpoints. Of note, in order to avoid potential confounding from differences in 24-hour viability of 42- vs 7-day RBCs, we only administered 85% of the 7-day RBC units, compared with 100% of the 42 day units. Therefore, these preliminary data should reflect differences in RBC quality/function and not RBC mass. Indeed, peripheral blood hemoglobin increased similarly ($p=0.6$) after transfusion of 2 units of 7- or 42-day RBCs using this protocol. To our knowledge, no previous study has demonstrated functional differences in oxygen delivery/exercise performance due to changes in RBC storage duration. We believe these preliminary data demonstrate the feasibility of using rigorous VO_2 max testing as an *in vivo* model for RBC function, and are proposing a larger more rigorous study to confirm these observed differences. In addition, the proposed study will contain a 3rd study arm (28-day storage). This will add valuable information that may help explain the RECESS Trial results.¹¹ Our hypothesis is that there is a difference in VO_2 max between the oldest RBCs (42-day) and fresh blood (7-day), but that, consistent with RECESS results, there is no difference in oxygen delivery between 7- and 28-day RBCs, which were the median duration of storage from the 2 RECESS study arms.¹¹

Before we describe our experimental approach we will present below general background information on VO_2 max testing and factors that affect it.

Maximal oxygen uptake (VO_2 max) testing: Background

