While VO_2 max can change with training and other interventions, it is remarkably constant over a period of days in the absence of any significant changes. For example, with a standardized protocol, i.e. absence of any interventions such as blood removal or transfusion, and use of the same “coach” to encourage the volunteers to exercise to exhaustion, VO_2 max test results show very little intra-subject variability over several days. Relevant data are below.^{26,40}

Serial VO_2 max tests on days 1 and 7 in 10 healthy volunteers show minimal intra-subject variability (Moon et al).

Serial VO_2 max tests over 5 days in 13 healthy volunteers show minimal intra-subject variability (Jamnik et al).

[figure not shown]
Therefore, the reproducible and quantitative nature of VO_2 max testing makes it ideal for studying interventions that may affect oxygen delivery.

VO_2 max: Previous Studies of Anemia/Hemoglobin Reduction and RBC Transfusion

As previously reviewed,^{39,40} numerous studies regarding the effects of blood removal and transfusion on VO_2 max and/or exercise performance have been performed, some as early as 1940.⁴¹ This research has been driven in part by an interest in “blood doping,” a technique used to improve exercise performance.^{39,40,42,43} Many studies report the effects of blood removal and transfusion on both exercise performance and VO_2 max; however, some report effects on only one of these outcomes.

Blood Removal: Gledhill and others have shown that a reduction in arterial oxygen content (specifically a reduction in hemoglobin) results in a reproducible decrease in VO_2 max.⁴⁰ This is attributable to decreased arterial oxygen content,^{29,33,40} and not decreased cardiac output if VO_2 max is measured at least 48 hours after removal of blood in order to allow the total plasma volume to normalize.^{40,44,45} Indeed, for hemoglobin levels ranging from 11-16 g/dL, each decrease in hemoglobin of 0.3 g/dL results in a 1% decrease in VO_2 max.⁴⁰

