Each RBC unit will be weighed, and its volume will be calculated according to the Donor Center's standard formula: red cell volume (mL) without AS-3 = product weight/1.08.

RBC units will be stored in the blood bank under standard conditions (1°C -6°C) and under the supervision of its medical director ([name], Co-Investigator).

MONDAY of Week 6: VO₂ max Test (Baseline)

During week 6 of each cycle, the VO₂ max test on Monday will serve as the "baseline" for changes in VO₂ max measured on Friday (primary endpoint) and Wednesday (secondary endpoint) of that same week. Although we are targeting mild anemia for this visit (Hb 11-12 g/dL), it is probably not critical that we achieve a certain hemoglobin level before transfusion since previous studies have shown increases in VO₂ max for a very wide range of Hb levels, i.e. up to 16 g/dL.^{44,45,48-50}

WEDNESDAY of Week 6: Blood Transfusion and VO₂ max Testing

We will use the same procedures for transfusing autologous stored RBCs that we used successfully in our recently completed pilot study and TASER study.²⁴ Procedures (details below) have been designed to optimize safety of research subjects.

Before the subject's visit, a sterile welding device will be used to remove a small aliquot from each RBC unit. This aliquot will be sent to Stony Brook Hospital's Microbiology Laboratory for culture to rule out potential bacterial contamination of a stored unit. Based on *in-vivo* viability at 24 hours after transfusion,⁵² we anticipate that transfusion of 100% of 42-day RBCs, 95% of 28-day RBCs, and 85% of 7-day RBCs, will generally compensate for differences in post-transfusion 24-hour viability. In order to confirm that this adjustment is appropriate, we will measure the Hb levels for each subject before and after transfusion, and 2 days later (Friday visit) to ensure that there are no differences in RBC mass that could confound the results. In the unlikely event that this is an issue, our statistician can adjust for this potential interaction.

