To minimize variability in VO_2 max testing procedures, the same facilitator ([name]- Study Coordinator) will be present at every test. To further minimize variability, subjects will be required to avoid moderate or heavy exercise the weekend before week 6 and during the week of testing (week 6), which will eliminate the risk for confounding from recent strenuous exercise, e.g. a 10-mile run the day before testing.

Additional Measurements During VO_2 max Testing

On 2 of the visits for VO_2 max testing (Monday and Friday for our primary endpoint), peripheral blood Hb will be measured before each VO_2 max test to confirm that our strategy for ensuring similar RBC mass between

study arms (7-, 28-, 42-days) has been effective. If necessary our statistician can correct for a possible interaction.

Subject Payment

Subjects will be paid for each study visit that they complete: \$50 for completing screening visit, \$50 for completing each of the two blood donation visits, \$50 for completing the day 40 exercise test visit, \$150 for completing the transfusion and exercise test visit and \$350 after completing the final visit of exercise testing

E. STATISTICS

Randomization and Allocation Concealment: The pattern randomization scheme will be generated using a computer algorithm. Transfusion Services personnel will assign each subject to an administration sequence (above) using a sealed envelope technique. Subjects will be randomized to receive 7-, 28- or 42-day-old blood at the time of their enrollment.

Statistical Analyses: All analyses will be conducted by the team's biostatistician ([name]). Summary statistics, including 95% confidence intervals, will be reported on all demographic and outcome data collected, including all multiple hemoglobin and VO₂ max measures.

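### Does the unnamed hemoglobin value in the supportive regression, with optional correction mentioned elsewhere, call for a change to the plan?

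*Combined protocol and SAP*

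**What the plan says.** Section E (Statistics), primary outcome, compares proportional change in VO2 max between the 7- and 42-day arms by t-test or Wilcoxon rank sum test, as a "one sided superiority hypothesis test at the 0.05 significance level". No covariate enters that test. The same paragraph then commits, without any condition, to a further look at the treatment effect by "adjusting for potential effects of hemoglobin, and BMI in a linear regression model".

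Two procedural paragraphs in Section D.5 also touch on Hb:

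- **Wednesday of Week 6.** Hb is measured before and after transfusion and again on Friday, "to ensure that there are no differences in RBC mass that could confound the results". The text adds: "In the unlikely event that this is an issue, our statistician can adjust for this potential interaction".
- **Additional Measurements During VO2 max Testing.** On Monday and Friday, "peripheral blood Hb will be measured before each VO_2 max test", as a check that RBC mass is similar across all three arms. It adds: "If necessary our statistician can correct for a possible interaction".

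Section C (Preliminary Studies) explains the interest in Hb. Because the share of each unit transfused was set to offset viability losses, the pilot authors argue that "these preliminary data should reflect differences in RBC quality/function and not RBC mass". Section E also promises summary statistics with 95% confidence intervals for every Hb and VO2 max measurement.

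**The concern.** Read together, these paragraphs seem to disagree. Section E adjusts for Hb in any event; Section D.5 adjusts only if a problem appears, and gives no criterion for one. Hb is available on Monday, before and after transfusion on Wednesday, and on Friday, and no paragraph says which value, or which change, is the covariate. Section D.5 speaks of an interaction where Section E describes covariate adjustment.

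The candidate covariates also answer different questions. Monday Hb is a baseline value, so adjusting for it leaves the total effect of storage age as the target. Hb change from Monday to Friday is measured after transfusion, and adjusting for it aims at the effect given equal Hb rise. The trial's interpretation is that any deficit reflects cell function and not cell mass. If the covariate were picked after the data were seen, the analysis closest to that interpretation could be steered towards the preferred answer.

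**Working it through.** **1. The plan's own figure.** Inputs from Section E (Sample Size): means 8.7% and 1.6%, SD 6%, one-sided 0.05, power 80%.

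- Difference: 8.7 - 1.6 = 7.1 points. Effect size: 7.1/6 = 1.183, as stated.
- Noncentrality at 10 per arm: 7.1/(6 x sqrt(2/10)) = 2.646. With 18 df and critical value 1.734, exact power is 81.6%. With 9 per arm it is 77.5%.

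The stated 10 per arm reproduces, and no Hb choice enters it.

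**2. How far the covariate could move the supportive estimate.** The slope comes from Section C (Blood Removal paragraph): "each decrease in hemoglobin of 0.3 g/dL results in a 1% decrease in VO_2 max", or 1/0.3 points per g/dL. The documents give no Hb SDs and no expected difference in Hb rise, so these are assumed: Monday SD (sM) 0.5-1.0 g/dL, SD of the rise (sR) 0.3-0.7 g/dL, and a 42-day rise lower by d = 0.3 or 0.5 g/dL. With one common slope, the cut from 7.1 is:

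- Monday Hb: 0.
- Hb change: d/0.3.
- Friday Hb alone: (d/0.3) x sR²/(sM² + sR²). At d = 0.3, sM = 0.75, sR = 0.5 this is 1.0 x 0.25/0.8125 = 0.31.

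| Covariate | d = 0 | d = 0.3 | d = 0.5 |
|---|---|---|---|
| Monday Hb | 7.1 | 7.1 | 7.1 |
| Friday Hb alone | 7.1 | 6.4-7.0 | 6.0-7.0 |
| Hb change | 7.1 | 6.1 | 5.4 |

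These are averages. The only evidence on d in the documents is the pilot, where Hb rose similarly in both arms (p = 0.6, 4 per arm). That is compatible with d = 0 but does not establish it.

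**3. Dependence on the common slope.** If 42-day cells deliver less oxygen per g/dL, which is the hypothesis, the slopes differ by arm. Assume a 7-day rise of 8.7 x 0.3 = 2.61 g/dL, and that all of each arm's gain comes through Hb.

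- d = 0.3: the 42-day slope is 1.6/2.31 = 0.69; the average slope is (3.33 + 0.69)/2 = 2.01; the Hb-change estimate is 7.1 - 0.3 x 2.01 = 6.5.
- d = 0.5: the 42-day slope is 1.6/2.11 = 0.76; the average slope is 2.05; the estimate is 7.1 - 0.5 x 2.05 = 6.1.

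So 6.1 and 5.4 become 6.5 and 6.1 under another reasonable model.

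**4. Choosing among the three models.** In simulation with no storage effect and equal Hb rises (same assumed SDs, slope from Section C), each single model rejects in about 5% of trials. Taking the most favourable of Monday, Friday and change rejects in 6.6-7.5%. The three estimates span a median of 0.6-1.0 points within a trial, and 1.9-2.6 at the 90th percentile.

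**5. What the Hb check can show.** The 95% CI half-width for the difference in Hb rise at 10 per arm is 2.101 x sR x sqrt(0.2): 0.28, 0.47 or 0.66 g/dL for sR = 0.3, 0.5 or 0.7. Divided by 0.3, that is 0.9, 1.6 or 2.2 points, or 13%, 22% or 31% of 7.1.

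**6. The paragraphs side by side.** Section E is the statistics section and commits to a supportive 7- versus 42-day regression. Section D.5 describes a procedural check of RBC mass and says what the statistician is able to do if it fails. A committed regression and an optional further correction can coexist. As Section E specifies the primary test without covariates and introduces the regression as a further step, its natural place is beside the primary result.

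**The case for a change.** The strongest case for a change is that the Hb-adjusted result is the one closest to the claim of function rather than mass, yet it is the least specified. On the plan's own slope, 0.3 g/dL is worth 1.0 of the 7.1 points (14%) and 0.5 g/dL is worth 1.7 (23%). A pilot p-value of 0.6 with 4 per arm does not show equal rises, and step 5 shows that 10 per arm cannot ensure them either. Naming the covariate would cost only a sentence.

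Much of this stands as description: the covariate is unnamed, Section D.5 gives no trigger or model form, and its word for ensuring equal mass is too strong. It does not carry the case for a change, for three reasons.

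- The 6.6-7.5% rate applies only if a supportive regression is used as a hypothesis test. The primary test's error rate is untouched.
- No single specification is clearly better. Monday Hb moves the average estimate by nothing and has about 77% power in simulation, against 81.6% for the primary test. Hb change conditions on a post-transfusion value, imposes a common slope that the hypothesis may contradict, and uses a concentration as a proxy for mass. Its power is 58-70% at d = 0.3.
- Calling the correction an interaction may be loose wording, but it is not plainly wrong. If storage lowers the VO2 max gained per g/dL, an arm-by-Hb-change interaction is what one would expect.

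**Conclusion.** No change is needed. This is a missing detail in a supportive analysis, not a contradiction between sections. The primary test, the 10 per arm and the 81.6% power do not depend on it. Under a common slope, the supportive estimate could vary between 6.1 and 7.1 points at an assumed 0.3 g/dL difference in Hb rise, and between 5.4 and 7.1 at 0.5 g/dL; with equal rises the choices agree on average. All of these figures rest on assumed Hb SDs and differences, and on a slope that Section C reports for Hb reduction after blood removal.

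Selective presentation is also limited. Section E commits to the regression whatever the Hb check shows, and to reporting all Hb measures with 95% confidence intervals. It does not name the between-arm difference in Hb change, but a reader would see Hb by time point. An analyst can fill the gap in the ordinary way: state which Hb value was used, treat any model with post-transfusion Hb as explanatory, and present it as an estimate with its interval beside the unadjusted primary result.
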